#### Medication Recording Requirements

Prior and concomitant medications taken for PBC, including UDCA, OCA, fenofibrate or bezafibrate, will be recorded up to the end of the EoT Visit in the appropriate section of the eCRF.

All other medication (including vaccines, over-the-counter or prescription medicines, vitamins, and/or herbal supplements) taken from 3 months (90 days) before Screening Visit 1 until the end of the EoT Visit will also be recorded in the appropriate section of the eCRF.

The following details must be recorded in the eCRF:

- Medication name, ideally the generic name
- Reason for use
- Start and end date of administration
- The dose and frequency of administration

In addition, the following details of medications taken for PBC, will be recorded in the eCRF:

- Prior use of OCA (yes/no), fenofibrate (yes/no), bezafibrate (yes/no)
- Reason for dose change (only concomitant medications taken for PBC)
- Reason for discontinuing prior or concomitant medications taken for PBC

The Medical Monitor should be contacted if there are any questions regarding prior or concomitant medication or procedures.

#### 6.8 Overdose

For this study, a single intake of 5 or more setanaxib tablets and/or a total daily dose of 7 or more tablets will be considered an overdose.

The Sponsor does not recommend specific treatment for an overdose with setanaxib.

Decisions regarding dose interruptions will be made by the Investigator based on the clinical evaluation of the patient.

In the event of an overdose, patients should be closely observed/hospitalized for close observation and appropriate symptomatic/supportive medical care and be followed until resolution/stabilization of any clinical issues.

Any instance of overdose (suspected or confirmed and irrespective of whether or not it involved setanaxib) must be communicated to the Sponsor (or a specified designee) using the overdose report form within 24 hours of becoming aware of its occurrence.

Any overdose associated with clinical symptoms will be recorded as an AE or SAE, as appropriate. Note that an overdose without clinical symptoms will not be recorded as an AE or SAE, even if the patient was hospitalized for observation. Details of any signs or symptoms and their management should be recorded, including details of any treatments administered for the overdose. All overdoses with clinical symptoms meeting the SAE criteria must be reported as described in Section 7.4.

#### 6.9 Compliance

The Investigator (or designee) will explain the correct use of the IMP to each patient and will check that each patient is following the instructions properly. Patients will document the IMP doses that they take on a patient IMP dosing card.

Compliance will be assessed at each visit by counting the returned tablets and will be documented in the source documents and eCRF. Any deviation from the correct use of the IMP will be recorded in the eCRF.

A record of the number of IMP tablets dispensed to and taken by each patient will be maintained and reconciled with IMP and compliance records. The IMP start and stop dates, including dates for IMP interruptions, will also be recorded in the eCRF.

#### 6.10 Accountability

The IMP must not be used for any purpose other than that defined in this protocol. All supplies of IMP will be accounted for in accordance with Good Clinical Practice (GCP).

The pharmacist (or designee) should maintain accurate records of all IMP supplies received during the study. These records should include the dates and amounts of IMP that were received at the site, dispensed, and destroyed or returned to the Sponsor (or designee). The records should include dates, quantities, batch/serial numbers, expiration dates (if applicable), and the unique code numbers assigned to the IMP and study patients. If errors or damage in the IMP shipments occur, the Investigator should contact the Sponsor (or its designee) immediately. Copies of the IMP accountability records will be provided by each Investigator for inclusion in the trial master file. The study monitor will periodically check the supplies of IMP held by the Investigator or pharmacist to verify accountability of the IMP used.

The Investigator (or designee) will dispense the IMP only to the identified patients in this study, according to the procedures described in this study protocol. Details of IMP dispensed to patients, will be recorded in the eCRF. Investigators should maintain records that document adequately that the patients were provided the doses specified by the protocol and reconcile all IMP received from the Sponsor (or designee).

After the end of the study, all unused IMP and all medication containers should be destroyed at the study center or returned to the drug depot for destruction, as instructed

in the pharmacy manual. In either instance, complete documentation will be returned to the Sponsor (or designee). The IMP resupply will be managed by the IXRS.

## 7 ADVERSE EVENTS

#### 7.1 **Definitions**

### 7.1.1 Adverse Events

An AE is any untoward medical occurrence in a patient or clinical study patient administered a pharmaceutical product and which does not necessarily have a causal relationship with this treatment. An AE can therefore be any unfavorable and unintended sign (including an abnormal laboratory finding), symptom, or disease temporally associated with the use of a medicinal (investigational) product, whether or not related to the medicinal (investigational) product.

#### 7.1.2 Serious Adverse Events

An SAE is any event that meets any of the following criteria:

- Results in death (Investigators should identify 1 SAE that is the leading cause of death).
- Is life-threatening.
- Requires inpatient hospitalization or prolongation of existing hospitalization.
- Results in persistent or significant disability/incapacity.
- Is a congenital anomaly/birth defect.
- Is an important medical event that may not result in death, be life-threatening, or require hospitalization. The event will be considered an SAE when, based upon appropriate medical and scientific judgment, the event may jeopardize the patient and may require medical or surgical intervention to prevent one of the outcomes listed above. Examples of such events include intensive treatment in an emergency room or at home for allergic bronchospasm, blood dyscrasias or convulsions that do not result in inpatient hospitalization, or the development of drug dependency or drug abuse.

#### **Definition of Terms**

Life-threatening: an AE is life-threatening if the patient was at immediate risk of death from the event as it occurred, i.e., it does not include a reaction that, if it had occurred in a more severe form, might have caused death. For example, drug-induced hepatitis that resolved without evidence of hepatic failure would not be considered life-threatening even though drug-induced hepatitis can be fatal. It does not include an AE or suspected adverse reaction that, had it occurred in a more severe form, might have caused death.

Hospitalization: AEs requiring hospitalization should be considered SAEs. Hospitalization for elective surgery, or for procedures planned prior to the patient providing informed consent, or routine clinical procedures that are not the result of an AE (eg, elective surgery for a pre-existing condition that has not worsened) need not be considered AEs or SAEs. If anything untoward is reported during the procedure, that occurrence must be reported as an AE, either 'serious' or 'nonserious' according to the usual criteria.

In general, hospitalization signifies that the patient has been detained (usually involving at least an overnight stay) at the hospital or emergency ward for observation and/or treatment that would not have been appropriate in the physician's office or outpatient setting. When in doubt as to whether hospitalization occurred or was necessary, the AE should be considered serious.

Disability/incapacity: an AE is incapacitating or disabling if the experience results in a substantial and/or permanent disruption of the patient's ability to carry out normal life functions.

#### 7.1.3 Suspected Unexpected Serious Adverse Reactions

A suspected unexpected serious adverse reaction is defined as an untoward and unintended response to a study drug, which is not listed in the applicable product information (eg, IB for an unapproved IMP or the SmPC [Summary of Product Characteristics] for an authorized medicinal product), and meets one of the following serious criteria: results in death, is life-threatening, requires hospitalization or prolongation of an existing hospitalization, results in persistent or significant disability or incapacity, is a congenital anomaly or birth defect, or is an important medical event that may not result in death, be life-threatening, or require hospitalization; and is assessed as causally related to the IMP. For suspected unexpected serious adverse reactions, the blind will be broken for safety reporting purposes.

#### 7.1.4 Clinical Laboratory Abnormalities and Other Abnormal Assessments

Laboratory abnormalities without clinical significance should not be recorded as AEs or SAEs. However, clinically significant laboratory abnormalities as per the Investigator's assessment (eg, clinical chemistry, hematology, and urinalysis abnormalities) that require medical or surgical intervention or lead to IMP interruption or discontinuation must be recorded as an AE or SAE, as applicable. In addition, laboratory or other abnormal assessments (eg, in ECGs, X-rays, or vital signs) that are associated with signs and/or symptoms must be recorded as an AE or SAE if they meet the definition of an AE or SAE as described in Sections 7.1.1 and 7.1.2. Any worsening of existing abnormalities that are associated with signs and/or symptoms [see Section 7.3]) should be reported as AEs or SAEs, as appropriate. If the laboratory abnormality is part of a syndrome, record the syndrome or diagnosis (eg, anemia) as the AE or SAE, not the laboratory result (ie, decreased hemoglobin).

For specific information on handling of clinical laboratory abnormalities, see Section 5.3.2.

#### 7.1.5 Adverse Events of Special Interest

The AESIs for this study are DILI, anemia, and hypothyroidism.

AESIs of DILI will be defined as any DILI event that meets the criteria in **A**, **B**, or **C** of Appendix II. Please refer to Section 5.3.2.1 and Appendix II for details regarding the detection and management of cases of DILI.

AESIs of anemia will be defined as CTCAE Grade  $\geq 2$  anemia AND absolute reticulocyte counts of <50% of the Baseline value, which is confirmed by repeat testing. Please refer to Section 5.3.2.2 for details regarding the detection and management of potential cases of bone marrow toxicity.

AESIs of hypothyroidism will be defined as TSH levels of  $\geq 10$  mIU/L, which is confirmed by repeat testing at the central laboratory (ie, TSH  $\geq 10$  mIU/L and reduced free T4). Please refer to Section 5.3.2.3 for details regarding the detection and management of hypothyroidism. The AESI should be reported by the investigative site to the ICON Drug Safety Center within 24 hours of learning about the event by completing the paper safety report form and sending it via email or fax. The documentation and processing of AESIs is further detailed in the Investigator Site File.

The AESIs will be adjudicated by the Adjudication Committee (see Section 9.4.1).

Investigators will indicate on the relevant Adverse Event eCRF page if the event meets the criteria for an AESI. If the event meets the criteria for an AESI, the Investigator will inform the Sponsor (or designee) of the AESI utilizing the safety report form (refer to the SAE contact information at the beginning of this protocol) and will then complete the Adjudication Event eCRF.

Please refer to the Investigator adjudication manual for further information.

#### 7.2 Assessment of Adverse Events

#### 7.2.1 Severity

The terms serious and severe are not synonymous. The general term "severe" is often used to describe the intensity (severity) of a specific event; the event itself, however, may be of relatively minor medical significance (such as a Grade 3 headache). This is NOT the same as serious, which is usually associated with events that pose a threat to a patient's life or ability to function (see Section 7.1.2). A severe AE (classified as Grade 3) does not necessarily need to be considered serious. For example, a WBC count of 1000/mm^3 to less than 2000/mm^3 is considered Grade 3 (severe) but may not be considered serious. Seriousness (not intensity) serves as a guide for defining regulatory reporting obligations.

Investigators will grade all AEs by severity using CTCAE (version 4.03).

If an AE is not listed in the CTCAE criteria, a corresponding grading is to be performed by the Investigator based on his/her best medical judgment as follows:

• Mild (Grade 1): asymptomatic or mild symptoms; clinical or diagnostic observations only; intervention not indicated

- Moderate (Grade 2): minimal, local, or noninvasive intervention indicated; limited age-appropriate instrumental activities of daily living (ADL)
- Severe (Grade 3): medically significant but not immediately life-threatening; hospitalization or prolongation of hospitalization indicated; disabling; or limiting self-care ADL
- Life-threatening (Grade 4): life-threatening consequences; urgent intervention indicated
- Death (Grade 5): death related to an AE

#### 7.2.2 Causality

Investigators are required to systematically assess the causal relationship between the AEs and SAEs and the exposure to the IMP using the following definitions:

#### **Related:**

- The AE has a reasonable possibility of an association with the product because:
  - The AE follows a reasonable temporal sequence to IMP administration and cannot be reasonably explained by the patient's clinical state or other risk factors (eg, disease under study, concurrent diseases, or concomitant medications).
  - The AE follows a reasonable temporal sequence to IMP administration, and it is a known reaction to the drug under study or a related chemical group or is predicted by known pharmacology or nonclinical safety.

#### Not Related:

• The AE does not follow a reasonable sequence from IMP administration, or it can be reasonably explained by the patient's clinical state or other factors (eg, disease under study, concurrent diseases, and concomitant medications).

#### 7.3 Documenting and Reporting Adverse Events

Reporting of AEs will begin when the patient has provided informed consent and will continue up to 30 days after the last IMP administration.

Occurrence of AEs may be volunteered spontaneously by the patient; discovered as a result of general, nonleading verbal questioning by the study staff; or determined by physical examination or other safety assessments. All AEs will be monitored and recorded in the eCRF throughout the entire study. Note that worsening of PBC-related pre-existing conditions will not be reported as AEs. Worsening of other existing abnormalities that are associated with signs and/or symptoms should be reported as AEs (or SAEs), as appropriate.

For all AEs, the Investigator must pursue and obtain adequate information (a description of the event, severity, time of occurrence, including whether the AE onset was before, during, or after the IMP administration if the AE started on a dosing day, duration, and any action, eg, treatment/follow-up tests). The outcome of the event should be provided along with the Investigator's assessment of the relationship to the IMP. The Investigator must also assess whether the event meets the criteria for classification as an SAE.

It is the Investigator's responsibility to review all documentation (eg, hospital notes, laboratory reports, and diagnostic reports) related to an AE. Wherever possible, the Investigator's diagnosis, not the individual signs and symptoms, will be documented as the AE.

Investigators are not obligated to actively seek AEs or SAEs after the patient's conclusion of study participation. However, if the Investigator learns of any SAE, including death, at any time after a patient has been discharged from the study, and he/she considers the event to be reasonably related to the IMP or study participation, the Investigator must promptly notify the Sponsor (or designee).

## 7.4 **Reporting of Serious Adverse Events**

For SAEs with an onset inside the reporting period (ie, onset after provision of informed consent and up to 30 days after the last IMP administration), the Investigator must immediately, without undue delay but under no circumstances no later than 24 hours after becoming aware of the event, inform the Sponsor (or designee) of the SAE utilizing the safety report form (refer to the SAE contact information at the beginning of this protocol).

The Investigator is obliged to respond to any request for follow-up information (eg, additional information, event outcome, final evaluation, or other records where needed) or to any question the Sponsor (or designee) may have concerning the SAE within the same timelines as those noted above for initial reports. This is necessary to ensure prompt assessment of the event by the Sponsor (or designee) and, as applicable, to allow the Sponsor to meet strict regulatory timelines associated with expedited reporting obligations for events of this nature.

## 7.5 Adverse Event and Serious Adverse Event Follow-up

During the study (and after the patient's participation in the study has ended), all AEs and SAEs should be followed proactively by the Investigator until the event resolves or the condition stabilizes to a level acceptable to the Investigator, until the event is otherwise explained, or until the patient is lost to follow-up. At the time the patient's study participation ends, all ongoing AEs and SAEs should be evaluated for resolution. New or updated information will be recorded in the originally completed eCRF and the Investigator will submit any updated SAE/AESI information to the Sponsor (or designee) within the same timelines as those noted above for initial reports after receipt of the information.

## 7.6 Safety Reporting Oversight

In accordance with ICH GCP, the Sponsor (or designee) will inform Investigators of "findings that could affect adversely the safety of patients, impact the conduct of the study, or alter the IEC/IRB's approval/favorable opinion to continue the trial."

The Sponsor (or designee) has a legal responsibility to notify both the local regulatory authority and other regulatory agencies about the safety of an IMP under clinical investigation. The Sponsor (or designee) will comply with country-specific regulatory requirements relating to safety reporting to the regulatory authority, IRB/IEC, and Investigators. To support compliance with these requirements, the Investigator must provide requested information in a timely manner.

An Investigator who receives an Investigator safety report describing SAEs or other specific safety information (eg, summary or listing of SAEs) from the Sponsor (or designee) will file it along with the IB and will notify the IRB/IEC, if appropriate, according to local requirements.

## 8 STATISTICS

## 8.1 General Procedures

With the exception of the unblinded statistician and programmers supporting the IDMC, all personnel involved with the analysis of the study will remain blinded until database lock and identification of protocol deviations. Analyses will be performed using SAS® (SAS Institute, Cary, NC, US) by the Sponsor or its representatives.

A detailed description of all statistical analyses to be performed for this study and any deviations from the analysis detailed in the protocol will be outlined in the Statistical Analysis Plan (SAP). A first version of the SAP will be prepared prior to the inclusion of the first study patient and the SAP will be approved prior to database lock.

All data will be presented by treatment group. Descriptive statistics (number of observations, mean, SD, median, minimum, and maximum) will be provided for continuous variables, and counts and percentages will be presented for categorical variables.

For the primary endpoint of change in ALP (%), Baseline is defined as the last nonmissing measurement prior to the first administration of study drug, or, if multiple pretreatment measurements are available, the arithmetic mean of the last (up to) 3 measurements preceding the first administration of study drug. This includes unscheduled and screening visits. For rescreened patients, the value associated with their screen failure record will not be considered for Baseline. If a patient has a Screening Visit 2 due to a retest for ALP, the last nonmissing measurement prior to the first administration of study drug will be used as Baseline for the efficacy analyses.

For other endpoints, Baseline will be defined as the last nonmissing measurement before or on the date of first administration of IMP, unless otherwise stated in the SAP.

The primary analysis will include data collected over a 24-week Double-blind Treatment Period. Any data collected after Week 24 (and a 4-week Follow-up Period) will be listed and, where sufficient data are available, may be summarized.

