6.1 Changes from Protocol

 Protocol Amendment version 5.0 Section 8.2: the definition of PPS is more clearly defined as all subjects in the FAS who do not have any important protocol deviations during the 24-week treatment period that would potentially affect the efficacy of the study drug.

 Protocol Amendment version 5.0 Section 8.4.2 states that "Abnormal laboratory values will be listed by subject and summaries of the incidence and frequency by treatment group, scheduled visit, severity, and relationship to IMP will be presented." Clinically significant abnormalities will be recorded as an adverse event (AE) and the severity/relationship to investigational medicinal product (IMP) will be recorded on the AE CRF page. However specific summaries of other abnormal laboratory values will not contain the assessment of relationship to the IMP or severity as this will not be collected in the laboratory database.

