10.0 Conventions and Derivations

10.1 Baseline and Change from Baseline

10.1.1 Baseline Values for Liver Biochemistry

Baseline values for liver biochemistry (ALP, ALT, AST, total and direct bilirubin, and GGT) are determined by the geometric mean of the last (up to) 3 measurements preceding the first administration of study drug. This includes unscheduled and screening visits. The formula for the geometric mean (GM) given three measurements a, b, and c is expressed as follows:

$$GM = \exp(\log(a) + \log(b) + \log(c)/3)$$

For subjects who have records for both Screening/Visit 1 and Baseline Visit 3, the baseline will be calculated as the geometric mean of these two values. If there is an additional unscheduled pre-dose result, the geometric mean will be calculated using up to three values.

For subjects who have records for Screening/Visit 1, Screening/Visit 2, and Baseline Visit 3, the Screening/Visit 1 result should be disregarded due to the subject's re-screening. The baseline should be calculated as the geometric mean of the Screening/Visit 2 and Baseline Visit 3 results. If there is an additional unscheduled pre-dose result, the geometric mean should include up to three values.

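### Protocol 8.1 and SAP 10.1.1 define baseline ALP for the primary endpoint differently, SAP 6.1 does not declare the change, and the SAP's retest rule slightly raises baseline in patients retested for low ALP

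*Protocol*

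**What the plan says.** **Protocol 8.1.** For the primary endpoint, when several pre-treatment values exist, baseline is "the arithmetic mean of the last (up to) 3 measurements preceding the first administration of study drug", counting screening and unscheduled visits. Values under a screen-failure record are left out. There is one exception. After a Screening Visit 2 held because of an ALP retest, "the last nonmissing measurement prior to the first administration of study drug will be used as Baseline for the efficacy analyses". That is normally the Day 1 value. The section lets the SAP override the baseline definition for other endpoints, but gives no such licence for primary-endpoint ALP.

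**SAP 10.1.1.** Liver biochemistry baselines, ALP included, "are determined by the geometric mean of the last (up to) 3 measurements preceding the first administration of study drug". If Visit 1, Visit 2 and Visit 3 results all exist, "the Screening/Visit 1 result should be disregarded due to the subject's re-screening". Then: "The baseline should be calculated as the geometric mean of the Screening/Visit 2 and Baseline Visit 3 results". An unscheduled pre-dose value can be added, up to three in total. The reason for Visit 2 plays no part.

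**SAP 6.1.** Two departures from the protocol are listed. One is that "the definition of PPS is more clearly defined as all subjects in the FAS" without important deviations; the other concerns summaries of abnormal laboratory values. Baseline ALP is not among them, although Protocol 8.1 says that deviations from the protocol's analysis will be set out in the SAP.

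**What Visit 2 is.** Protocol 4.3 allows a repeat sample at Visit 2 without the patient becoming a screen failure. Rescreening is a separate process with a new screening number. The repeat may be for ALP, bilirubin, ALT/AST, TSH or INR, and Protocol 5.1 adds liver stiffness.

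**The concern.** Baseline ALP enters the primary analysis twice: as the denominator of the log ratio and as a covariate (SAP 12.5.2.1). It is also the reference for the 15, 30, 40 and 70% reductions in the cholestasis responder criteria. A variable with that role should have one definition. Here a patient retested for ALP has a different baseline under each document, both in the type of mean and in the values used.

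The choice of values is the part that matters. A patient retested for ALP had Visit 1 below 1.67×ULN and entered because Visit 2 reached it. Leaving out the low value and averaging in the one that had to be high pushes baseline up. The later return toward the patient's usual level then looks like an ALP reduction, in any arm. If Visit 2 was done for another reason, such as bilirubin or ALT/AST, and ALP was drawn with the panel, the SAP discards a Visit 1 ALP against which nothing has been said.

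**Working it through.** The plan gives no figure on this point to reproduce, so the check is a comparison of rules, a worked example and a simulation.

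**1. The rules side by side**

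| Patient | Protocol 8.1 | SAP 10.1.1 |
|---|---|---|
| Visit 1 and Day 1 only | arithmetic mean of both | geometric mean of both |
| Visit 2 for ALP | last value (Day 1) | geometric mean of Visit 2 and Day 1 |
| Visit 2 for another reason, ALP drawn | arithmetic mean of all three | geometric mean of Visit 2 and Day 1 |

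**2. Type of mean.** For 300, 320 and 310, the arithmetic mean is 310.0 and the geometric mean is 309.9. This difference is negligible.

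**3. Worked example** (assumed values, ×ULN): Visit 1 = 1.60, Visit 2 = 1.75, Day 1 = 1.62.
- Protocol: 1.62.
- SAP: √(1.75 × 1.62) = 1.684, and 1.684/1.62 = 1.039, so 3.9% higher.
- Visit 2 alone, which is not the SAP rule: 1.75, or 8.0% higher.

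**4. Simulation.** From the documents: the 1.67×ULN threshold and the rules above. Assumed, because the documents do not give them: lognormal true ALP in two populations (A: median 2.0×ULN, log SD 0.3; B: median 2.2×ULN, log SD 0.4), within-patient CV of 8, 10 or 15%, independent readings, every Visit 1 failure retested, and Day 1 not selected on. There were 2,000,000 patients per setting. Retested means Visit 1 < 1.67 and Visit 2 ≥ 1.67. The table shows population A; B gives nearly the same bias.

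| Within-patient CV | 8% | 10% | 15% |
|---|---|---|---|
| SAP rule, bias in ALP-retested patients | +3.3% | +4.0% | +5.8% |
| Protocol rule (Day 1), bias | 0 | 0 | 0 |
| Geometric mean of all three, bias | −0.4% | −0.6% | −1.2% |
| ALP-retested share of eligible patients | 6.4% | 7.8% | 11% |

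In population B the shares are about 4.5, 5.5 and 8.0%.

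**5. Shift over all patients** = share × bias, SAP rule against protocol rule.
- CV 8%: 0.064 × 3.3% = 0.2%.
- CV 10%: 0.078 × 4.0% = 0.3%.
- CV 15%: 0.11 × 5.8% = 0.6%.

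Population B gives smaller values (0.055 × 4.1% = 0.2% at CV 10%).

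**6. Effect on one responder threshold.** With a baseline 4% too high, a true 12% fall reads as 1 − 0.88/1.04 = 15.4%, which passes the 15% criterion.

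**7. Precision.** At CV 10%, the error SD of the baseline in ALP-retested patients is about 10% for Day 1 alone, 6.5% for the SAP rule and 5.7% for the mean of all three.

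**The case against.** The best defence is that this is a documentation mismatch with little numerical consequence. Much of that stands. At CV 10% in population A, about 0.078 × 66 = 5 of 66 patients would be ALP retests. If ALP truly did not change, apparent reductions of 15% or more among them would be 15.0% under the SAP rule and 12.5% under the protocol rule, and 5 × 0.025 is about 0.1 patient in the trial. Patients who pass at Visit 1 also carry a small upward bias, which neither rule removes.

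There is also a fair reason to leave Visit 1 out after an ALP retest. Protocol 4.3 reserves the repeat for results the investigator thinks spurious, confounded or out of line with history. If Visit 1 really were 22% too low (an illustration), the geometric mean of all three would be about 8% too low, against +1.1 to +3.3% for the SAP rule. Putting Visit 1 back for everyone is therefore not clearly better. It belongs in a sensitivity analysis.

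Three stronger readings are tempting, and the documents do not support them:
- *The SAP keeps only the qualifying value.* It averages Visit 2 with Day 1, which roughly halves the inflation that Visit 2 alone would give.
- *The comparison with placebo is biased.* All the values are pre-dose, the rule is the same in every arm, and log baseline is a covariate.
- *The rule was chosen with the data in view.* SAP 6.0 says that blinded team members had no access to ALP values, and the rule is stated openly in 10.1.1.

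What the defence does not answer is that two definitions exist, the change is undeclared, and the stated reason for dropping Visit 1 is not what the protocol calls rescreening.

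**Conclusion.** The conflict between the two documents and the omission from SAP 6.1 are certain from the text. So is the wrong label: a Visit 2 retest takes place within one screening period. The upward shift holds in direction for patients retested because of low ALP, and only for them. Its size, about 4% (3.3 to 5.8%), rests on the assumed within-patient CV of 8 to 15%. The share of patients concerned, roughly 4 to 11%, also rests on the assumed populations and on every failure being retested; fewer retests would make it smaller.

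Over all patients the shift is well under 1%. It bears on within-arm percent change and on descriptive responder counts near a threshold. It is not a reason to doubt the between-arm test. The point should be corrected because the variable is central and the correction is cheap.

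**What to change.** State one rule in Protocol 8.1 and SAP 10.1.1:
- Baseline ALP is the geometric mean of the last up to three pre-dose values.
- Visit 1 is excluded only if Visit 2 was a retest because of ALP. In those patients, use a value not selected on the entry threshold, namely the protocol's last pre-dose value. Say what applies if Day 1 is missing, since the last value could then be the selected Visit 2 result.
- If Visit 2 had another reason, Visit 1 stays eligible for the mean.
- Values under an earlier screen-failure number are excluded.
- Replace the term re-screening with retest.

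List the change from Protocol 8.1 in SAP 6.1. Add a sensitivity analysis of the primary endpoint using the geometric mean of all pre-dose values, Visit 1 included. SAP 10.1.1 also covers ALT, AST, bilirubin and GGT, so it should say whether the ALP exception extends to them.

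In the same edit, check the printed geometric-mean formula. As it stands only the third logarithm is divided by 3; read literally, 300, 320 and 310 give about 650,000 instead of 309.9.

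The cost is wording in both documents and one extra model run, with no new data. The downside is a noisier baseline in the few ALP-retested patients: SD about 10% against 6.5% at CV 10%.
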